The HIV epidemic in Tanzania: The HIV prevalence in Tanzania is 4.7%. There are ~2.6 million Tanzanians currently living with HIV (29,32). HIV is the leading cause of **hospital admissions and death** in adults in Tanzania (33). In 2016, HIV caused 18% of all adult deaths (33,000) (22,33). We conducted studies on the prevalence of HIV infection in hospitalized patients at the Bugando Medical Center in Mwanza, Tanzania. Bugando is the major public hospital in Mwanza and provides 75% of all the in-patient and outpatient HIV care in the city. We documented that 2,393 (22%) of 11,045 hospitalized adults were HIV-infected (1). **HIV prevalence rates among hospitalized adults** in other sub-Saharan hospitals are similar, ranging from **22% to 60%**. These rates have not decreased in recent years (1–10). The in-hospital mortality of HIV-infected adults in Tanzania and other African countries ranges from 20–35% (1,4,10,14,34,35).

There is a **very high mortality rate** in HIV-infected adults in the **first 12 months after discharge** in Tanzania. We conducted a study of 172 HIV-infected adults consecutively admitted to the Bugando Medical Center in Mwanza in 2013 (14). Details of their HIV status and ART history are provided in **Table 1**. Of note, the median time on ART in the 60 people who defaulted in the past was **only 45 days**. The median age of the HIV-1 infected adults was 37 years and 45 (26%) died in the hospital. The 127 survivors were discharged an average of 7 days after admission and were referred to

HIV clinics.

Table 1: HIV and ART History of 172 HIV infected Patients Admitted to Bugando Medical Center*

New HIV Diagnosis	38 (22%)
Prior HIV Diagnosis	
ART never started	68 (40%)
ART default	60 (35%)
On ART at hospital admission	6 (3%)

* patients consecutively admitted Sept- Dec 2013

Of the 127 patients, only 80 (63%) attended an outpatient HIV clinic visit in the first month and only 76 (60%) were alive at 12 months. Among patients who survived at least one month, those who **failed to link** to the HIV clinic within one month were **5.8 times more likely to die** in the first year than those who did attend. **Other studies from Africa** have demonstrated post- hospital 1-year survival rates of only **50-75%** (11–13,16).

Figure 1. Map of Tanzania and Mwanza

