Study Enrollment, Randomization, and Study Intervention: The baseline questionnaires will be completed on the day prior to discharge. We will consecutively enroll 25-30 participants per month until we reach a sample size of 500 participants (18-month enrollment period). The research assistant will assign a unique study identification number to each participant, collect demographic and clinical data from the medical file, and administer a baseline questionnaire. Locator information will be obtained for the study participant and 2 designated contact persons. The designated contact persons will be friends or relatives who the research team can contact if the study participant is not available for a study visit. Our own work and the work of others has demonstrated that phone calls and messages are highly acceptable and effective as a means of communication with HIV-infected patients in East Africa (14,60). Cell phones are the primary means of communication in Tanzania, and >95% of patients or their families use phones.

After this baseline assessment, on the morning of hospital discharge, participants will be randomized to either the DARAJA social worker intervention or the control group in a 1:1 ratio using a computer generated random assignment. The **research coordinator, [name]**, will provide the computer generated random assignments to [name], the chief social worker, and the social worker assigned to the ward will see the participant for the first time in the hospital on the morning of discharge. The participant will be considered enrolled once randomization occurs.

All 500 participants in the trial will receive care according to current standard practice in Mwanza, which was described previously (**see section C.1. Current Standard of HIV Care in Mwanza**). In brief, ART is initiated in the hospital according to the WHO guidelines (15). For a subset of patients with TB or cryptococcal disease, ART may be deferred for 2 to 4 weeks to prevent immune complications. All HIV-infected adults receive a 30-minute counseling session before hospital discharge by a hospital nurse trained in HIV care. They receive detailed instructions regarding their medications and clinic appointments. Upon discharge, the hospital nurse escorts patients to the HIV clinic and helps them schedule an appointment within one week. The hospital nurse also takes the phone number of patients and calls them the night before their scheduled visit to encourage them to go to clinic.

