The **250** participants randomized to the DARAJA intervention group will meet with a social worker in the hospital on the morning of discharge as described previously (**see C.1 Pilot Study of DARAJA Social Worker Intervention**). The second visit will be in the home, and then there will be three subsequent visits either in the patient's home or in the outpatient HIV clinic during the ensuing 3 months (total of 5 social worker visits). Of note, the social worker will be blinded to those participants enrolled in the control group.

Research Schedule, Measures, and Outcomes: A research schedule with the timing of study visits, measures, and outcomes for all 500 participants is provided in **Table 3** on the next page. These are in addition to the routine care or DARAJA social worker visits. All 500 participants in both study groups (control and DARAJA) will have three face-to-face visits and six phone interviews with a research assistant over 24 months. The **enrollment, 12 month, and 24-month** visits will be **face-to-face**. At 3-month interval phone calls, the research assistant will interview the participant about health status, clinical visits, and psycho social factors. The data managers will also extract information on clinic attendance, medications, and laboratory studies from the HIV Clinic EMR every three months. We will continue follow-up for 24 months to measure sustainability of the intervention. A description of the primary and secondary outcomes for each of the study aims is provided below:

Survival: Deaths will be documented by four methods. **1)** If a study participant misses a visit or does not respond to a phone call, then the research assistant will telephone the contacts and inquire about the participant's status. **2)** If neither the study participant nor the designated contact persons are available, a home visit will be made by a field worker. **3)** If the family reports that the participant was hospitalized, we will review hospital records. **4)** Tanzania has a well-organized system for death certificates, and nearly 100% of people who die in Mwanza have a death certificate. We will obtain copies of death certificates for all participants who cannot be contacted or who are reported deceased by a family member. The final cause of death will be decided by an adjudication committee consisting of the PI, [name] and [name].

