Linkage and other steps in the HIV care continuum: Linkage will be defined as having at least one visit to the outpatient HIV clinic. Twelve-month retention will be defined as being alive and having a clinic visit between 11 and 13 months. Twenty-four-month retention will be alive with a visit between 23 and 25 months. Adherence will be measured with a 3-day recall questionnaire and by reviewing pharmacy refill records and calculating the proportion of prescribed days of ART which are actually picked up over time. HIV RNA levels are measured routinely at the Mwanza HIV clinic at 6, 12 and 24 months, and we will retrieve results from the EMR. HIV viral suppression will be defined as a plasma HIV RNA level <1,000 copies/ μ l (15). Participants who have \geq 1,000 copies/ μ l or who do not have plasma HIV RNA level measured will be considered **virologic failures**.

TABLE 3.
RESEARCH SCHEDULE, MEASURES, AND OUTCOMES

		Month of Research Visits								
		0	3	6	9	12	15	18	21	24
RESEARCH ASSISTANT COMMUNICATIONS										
Face-to-face visits		X				X			X	
Phone call			X	X	X		X	X	X	
DEMOGRAPHICS										
Age, sex, education		*	X							
Economic status (weekly income)		*	X			X			X	
MEDICAL HISTORY										
Date of HIV diagnosis		+	X							
Prior ART use		+	X							
WHO stage		+	X	X	X	X	X	X	X	
Physical measures (height, weight, blood pressure)		+	X			X			X	
Alcohol use (AUDIT) (65,67,68)		*	X			X			X	
Depression (PHQ-9) (64)		*	X			X			X	
PSYCHOSOCIAL FACTORS										
Employment (ARTAS Baseline and Follow-up Tools) (69)		*	X			X			X	
Traditional health beliefs (HIV Knowledge Questionnaire) (70,62)		*	X			X			X	
Self-efficacy (HIV – Adherence Self-Efficacy Scale) (71)		*	X			X			X	
Transportation (ARTAS Baseline and Follow-up Tools) (69)		*	X			X			X	
Stigma (AIDS-Related Stigma Scale) (72,73)		*	X			X			X	
Social support (SPS-10) (63)		*	X			X			X	
Perceived need for HIV services (ARV Medications Attitude Scale – 15) (74)		*	X			X			X	
Physical Weakness (SF-12) (75,66)		*	X			X			X	
PRIMARY OUTCOME										
Death		¢		X	X	X	X	X	X	
STEPS IN HIV CARE CONTINUUM										
Linkage to HIV clinic (date of first clinic visit)		+		X	X	X	X	X	X	
Retention (attendance at monthly clinic visit)		+		X	X	X	X	X	X	
ART adherence (3-day recall; pharmacy refills)		*+	X	X	X	X	X	X	X	
Plasma HIV-1 RNA level			X		X		X		X	
ACCEPTABILITY										
Qualitative interviews		§					X	X	X	
COST										
Number and type of health facility visits		*+	X	X	X	X	X	X	X	

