Laboratory or radiologic services utilized		*+	X	X	X	X	X	X	X	
Medications use (prescription, non-prescription, and herbal)		*+	X	X	X	X	X	X	X	
Staff time for social worker Intervention		\$	X	X	X	X	X	X	X	

* Research assistant administered questionnaire

+ Data abstract from the HIV Clinic EMR

¢ Deaths will be documented by phone calls, home visits, hospital records, and death certificates

\$ Timing of a subset of social worker visits; social workers will also log all time spent on intervention activities

§ Qualitative interviews conducted with a subset of study participants and health care workers

Factors from the Gelberg and Andersen Model: We will measure the eight factors of the Gelberg and Andersen Behavioral Model of Health Services Utilization for Vulnerable Populations at enrollment, 3 months, 12 months, and 24 months (18). The measurement tools are listed in Table 3 and have been translated into Kiswahili and used in prior studies in East Africa (61–66).

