Secondary Aim 2: Gelberg and Andersen Model. The factors in the Gelberg and Andersen Healthcare Utilization Model for Vulnerable Populations will be evaluated using **structural equation modeling** (SEM) to take into account modeling of interactions, nonlinearities, and correlated independent variables. *A priori*, we will create a path analysis of direct and indirect pathways in the Gelberg and Andersen Model domains of predisposing, enabling and need variables. Our model selection will be guided by Information criteria (e.g., AIC/BIC) along with methods for addressing model selection uncertainty provided in Preacher and Merkle (76). We will evaluate the effect of randomization arm upon factors and pathways associated with the primary outcome (survival) as well as secondary outcomes (linkage to HIV clinic). We will also perform **mediation analysis** to determine which factors from the Model act as mediators and moderators of the primary and secondary outcomes, allowing us to explore how and for whom the intervention worked. Short and longer mediation pathways will be tested such as the direct effect of increased self-efficacy on early linkage vs. the effect of increased self-efficacy leading to early linkage leading to survival. Moderation analysis will be conducted to identify (or rule out) potential differential intervention effects for selected subgroups such as whether the intervention is more effective in HIV-infected adults who were ART-naive vs. ART-experienced.

Secondary Aim 3: Acceptability and Barriers/Facilitators of Linkage: All qualitative interviews will be transcribed verbatim, translated in English, and then entered into qualitative software (e.g. Atlas-ti) for coding and analysis. A thematic coding scheme will be created following the main points of the interview guide. To ensure inter-rater reliability of 85%, using Cohen's Kappa (κ) index, [name] and her assistant will code the first five transcripts independently, and then compare their results, and discuss ambiguities and inadequacies in the coding scheme. Refinements to the coding scheme will be made via discussion between [name] and the PI. [name] and her assistant will then code a second set of 5 transcripts, and come together again to compare their results a second time, discuss remaining ambiguities, and achieve consensus in the coding scheme. Based on our previous experience, it is expected that an inter-rater reliability of 75% or

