forms on password-protected encrypted tablets into the NIH approved RedCap data management system. Data will be uploaded via the internet onto a secure password protected server at the Clinical and Translational Science Center (CTSC) at Weill Cornell Medicine in New York. The RedCap system is password protected and only senior investigators ([name], [name]), MITU data managers ([name], [name]) and statistician/economic analyst ([name], [name]) will have access to these data

c. Potential Risks

This study does not include any investigational medications or devices. The risks of this study include loss of confidentiality, social harms, and discomfort answering personal questions. We describe how we will protect against each risk in section 2.

- A. **Loss of Confidentiality:** There is a potential loss of confidentiality of information provided during the study including one's HIV status through participation in the study. Participants randomized to the social worker group will have their HIV status known to the social worker by the nature of the intervention. There is also a risk that the home visit made by the social worker could result in loss of confidentiality. These risks for loss of confidentiality will be documented in informed consent procedures. Participants randomized to the control arm are also at risk for loss of confidentiality if they fail to link to HIV primary care and their HIV disease progresses. We believe that the risk of loss of confidentiality is equal in the two study arms and the same as anyone receiving HIV care in Tanzania.
- B. **Social Harms:** HIV-infected adults are a stigmatized population who are at heightened risk of social harm. Participants may experience social stigma or incur harm because of identification in the intervention or control arm of a HIV-related study. Social harm due to study participation may include loss of privacy, social stigma from perception of being "high risk" of HIV, interference with employment, and discrimination from their family or general public. Of note, adults who participated in our **pilot study cited decreased stigma** associated with receiving support and education from a social worker.
- C. **Discomfort:** Participants will be asked to complete study questionnaires at baseline and at 12 months after enrollment. Questionnaires include topics that may be sensitive such alcohol use, family and social support, and income and education.

2. Adequacy of Protection Against Risks

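### The planned path from increased self-efficacy to early linkage has no score taken after randomization and before most linkage, so it cannot be read as mediation

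*Protocol*

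**What the plan says.** The Protocol (Data Analysis, Secondary Aim 2) plans structural equation modelling and mediation analysis of the eight Gelberg and Andersen factors. As examples it gives a direct effect of increased self-efficacy on early linkage, and a longer chain, "the effect of increased self-efficacy leading to early linkage leading to survival".

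On when the factors are measured:

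- Study Enrollment, Randomization, and Study Intervention: "The baseline questionnaires will be completed on the day prior to discharge". Randomization follows on the morning of discharge.
- Factors from the Gelberg and Andersen Model: the factors are measured "at enrollment, 3 months, 12 months, and 24 months".
- Research Schedule, Measures, and Outcomes: in the three-monthly calls, "the research assistant will interview the participant about health status, clinical visits, and psycho social factors".
- Potential Risks, item C (Discomfort): "Participants will be asked to complete study questionnaires at baseline and at 12 months after enrollment".

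On when linkage happens, the enrollment section has the nurse help patients book an appointment within a week. C.1 reports that 80 of 127 patients in the 2013 cohort "attended an outpatient HIV clinic visit in the first month". It also says that about 30% still fail to link within a month under current care, and that all 31 pilot participants linked in the first month. Linkage is defined as at least one clinic visit; early linkage is not defined.

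The SAP's secondary endpoints are the care-continuum outcomes. It contains no structural equation or mediation analysis, and it does not withdraw Secondary Aim 2.

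**The concern.** For self-efficacy to carry the effect of the intervention to linkage, it must be measured after randomization, so that the arm can have changed it, and before linkage, so that it can be a cause. The schedule has no such measurement. The baseline score precedes randomization and cannot show a change due to arm. The month-3 score comes after most first visits.

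Attending the clinic may itself raise confidence in managing treatment. A fitted path from the month-3 score to linkage could then report a consequence of linkage as its cause. Choosing among models by AIC or BIC, as planned, does not settle the direction of an arrow. The score also exists only for people alive and in contact at month 3. At stake is the trial's account of how the intervention works, which is one of its stated goals.

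**Working it through.** **1. Order of events for one participant.** Baseline questionnaire (day before discharge), randomization and first social worker session (morning of discharge), first clinic appointment (within one week), next factor measurement (month 3 at the earliest).

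**2. The Protocol's linkage figures.** 2013 cohort: 80/127 = 0.630, which reproduces the stated 63%. Current care: 100% − about 30% = about 70%. Pilot: 31/31 = 100%.

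**3. Linked by month 1**, as 250 × control rate + 250 × intervention rate:

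| Control | Intervention | Linked by month 1 | Not yet linked |
|---|---|---|---|
| 70% | 100% | 175 + 250 = 425 (85%) | 75, all control |
| 63% | 100% | 157.5 + 250 = 407.5 (81.5%) | 92.5, all control |
| 70% | 70% (no effect) | 350 (70%) | 150 |
| 63% | 63% (no effect) | 315 (63%) | 185 |

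The last column is an upper limit on those who could have a month-3 score before first linkage, because some of them will link or die between months 1 and 3. At the pilot rate they are all controls, so there is no arm contrast among them.

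**4. Could the reversed order mislead?** An illustrative simulation used 500 runs per setting and 250 per arm. All its inputs are assumptions:

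- Linkage is 95% versus 70% and independent of self-efficacy.
- The month-3 score is 0.5 × baseline (SD 1), plus a shift if linked, plus noise (SD 0.8).
- Death before month 3 is 3% if linked and 12% if not.

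Among survivors, linkage was regressed on arm, baseline score and month-3 score. The coefficient of the month-3 score was significant at 0.05 in 5% of runs with no shift, 79% with a shift of 0.3, 99.8% with 0.5 and 100% with 0.8. A path that does not exist would thus often be reported.

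**5. Who has no month-3 score?** Those who die or are lost before month 3. The documents do not give their number. To show a range only, Weibull curves were fixed at 75% and 90% survival at month 12. Deaths by month 3 are then n × (1 − S12^(0.25^k)):

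- Shape k = 1: 17.3 control + 6.5 intervention = 23.8, or 27% of the 87.5 deaths expected by month 12 (62.5 + 25).
- Shape k = 0.5: 33.5 + 12.8 = 46.3, or 53%.

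The shapes are assumed. Under both, the loss is unequal by arm.

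**The case against.** The strongest reply is that this is one example path in a secondary aim meant to explore mechanism. The aim also covers the arm's effect on the factors and moderation, for example by prior ART use, and neither needs this path. That stands, and it limits the point to paths from post-baseline factors to early linkage.

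Three stronger readings are tempting, and the documents do not support them.

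- *The whole chain is lost, including linkage to survival.* The chain fails because its first leg fails. First visits and deaths are both dated, so the linkage-to-survival leg can be estimated, for example from a month-1 landmark.
- *No follow-up score exists for the roughly 88 of 500 expected to die within the year (25 + 62.5).* This needs month 12 to be the first re-measurement. It rests on the Discomfort paragraph, which describes risks, does not say that these are the only times, and omits the 24-month assessment scheduled elsewhere. The section that defines factor measurement names month 3, and the text on the three-monthly calls agrees. Table 3 could not be read column by column with confidence, so nothing here rests on it.
- *Most deaths precede month 3.* No document gives a count. The 27% to 53% above comes from assumed curves.

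Two possible defences do not help. The Missing Data section offers censoring, imputation of Cox covariates and missing-not-at-random sensitivity analyses, none of which changes time order; a score after death is undefined, not missing. The SAP's silence neither repairs nor retires the path.

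**Conclusion.** The point holds in a narrow form. The leg from increased self-efficacy to early linkage, and with it the full chain to survival, cannot be read as mediation, because no score is taken after randomization and before most linkage. At about 70% control and 100% intervention linkage, 85% of participants have linked before any follow-up score; across the Protocol's rates the figure is 63% to 85%. This assumes that the earlier cohort, current-care and pilot rates carry over to the trial. The conclusion on order holds whether the first re-measurement is at month 3 or month 12. If it is month 12, the factors also cannot mediate 12-month survival, since only survivors would have a score. The primary analysis is unaffected. The change is worth making because it is cheap and prevents a wrong conclusion about mechanism.

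**What to change.** In Secondary Aim 2, and in any analysis plan written for it:

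1. Remove the paths from post-baseline factors to early linkage, or report them only as associations. Define early linkage.
2. Keep baseline factors as predictors and as moderators of linkage. They precede linkage, so time order gives no reason to drop them.
3. Use month-3 factors as mediators only for outcomes after month 3, from a month-3 landmark. Treat linkage before month 3 as an earlier variable affected by arm, that is, a confounder of mediator and outcome that treatment itself changes. Ordinary path coefficients do not resolve such confounding, so the model must address it explicitly. Label the results exploratory among month-3 survivors.
4. Reconcile the Discomfort paragraph (baseline and 12 months) with the factor-measurement section and the text on the three-monthly calls, and check Table 3 against them. If month 12 is the first re-measurement, drop the factors as mediators of 12-month survival.

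A short self-efficacy measure between the first session and the first clinic visit would have closed the gap. The SAP describes the end-line survey as already conducted, so that is no longer open for this trial.

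The cost is rewording. Early deaths would not contribute to the mediation models, and the landmark sample is selected on survival, possibly unequally by arm. Both limits should be stated with the results.
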